Protocol Title

Lung Transplantation in Chronic Hepatitis C Infection with Post Transplant EPCLUSA Treatment: A Pilot Feasibility and Efficacy Study

Purpose of the Study

Primary objectives

- Assess feasibility, safety and efficacy of Epclusa treatment after lung transplant in those with chronic Hepatitis C Virus infection.
- Establish Sustained Virologic Response (SVR)12 rates in HCV-infected lung transplant recipients treated with EPCLUSA. SVR 12 is the absence of detectable hepatitis C virus in the blood after 12 weeks of antiviral therapy. This is the standard outcome in studies evaluating therapies to treat hepatitis C virus.

Secondary Objective

- Evaluate impact of considering donors who are hepatitis C nucleic acid amplification test (NAT) positive in recipients with pre-existing hepatitis C viremia on wait times and post transplant survival.
 - Are wait times shortened by considering HCV NAT positive donors?
 - Do HCV NAT positive donors otherwise meet criteria for lung donation?

Primary endpoints

- Sustained Virologic Response 12 weeks (SVR 12) in those treated with EPCLUSA
- Adverse events resulting in discontinuation of EPCLUSA
- Eligibility for EPCLUSA treatment within 12 months of lung transplant.
 - If subjects do not have adequate renal function or require medications with significant drug interactions with epclusa, they will not be eligible for treatment. Eligibility is an outcome because it is not known if these factors will limit utility of epclusa in this setting due to common complications associated with lung transplantation.

Secondary endpoints

- Serum HCV RNA levels at 12-, 24-, and 48-weeks after initiation of EPCLUSA
- Adverse events requiring temporary interruption in Epclusa therapy
- 90-day and 1-year post transplant patient survival
- 90-day and 1-year post transplant patient survival in recipients of HCV NAT positive donor organ

Exploratory outcomes

- Change in transient elastography score at 48-weeks post Epclusa treatment

- Acute rejection rates
- Primary graft dysfunction scores
- Infections requiring treatment
- Wait times associated with donor HCV status

Background & Significance

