Epclusa is a fixed-dose combination product containing sofosbuvir, an HCV NS5B polymerase inhibitor, and velpatasvir, an HCV NS5A inhibitor. It was approved by the FDA in June 2016 for the treatment of chronic HCV genotypes 1, 2, 3, 4, 5 and 6. The first antiviral approved to treat all major forms of HCV, it can be used in patients with compensated and uncompensated cirrhosis, as well as those without cirrhosis. Response rates, defined as a RCV RNA pcr less than the lower limit of quantification (<LLOQ) 12 weeks after completion of therapy (SVR12), in those without decompensated cirrhosis who were treated for 12 weeks range from 94-99%. It is recommended as first line therapy by the American Association for the Study of Liver Diseases (AASLD) and the Infectious Diseases Society of America (ISDA) for treatment of chronic HCV infection with genotypes 1, 2, 3, 4, 5 and 6.

The goal of this study is to assess whether a strategy of performing lung transplant in individuals with end stage lung disease and chronic HCV infection, and then treating them post-transplant with Epclusa is feasible, safe and effective at curing HCV.

The reason to wait until after lung transplant to treat the hepatitis C virus is two-fold. First, it opens up the donor pool to include those with chronic hepatitis C. This can potentially shorten wait times and increase the number of lungs used for transplantation, which could increase access to a life-saving transplant and for those suffering with end stage lung disease and decrease deaths on the waiting list. The second reason to adopt this strategy is that it allows those with rapidly progressive lung disease to be transplanted prior to completing 12 weeks of antiviral

therapy, during which time their lung disease might progress to the point where they are too sick to survive a lung transplant.

As a first step, this study includes only lung transplant candidates with chronic HCV infection. For these candidates with chronic HCV infection, consideration would be given to organ offers from both HCV NAT positive and HCV NAT negative donors. Donors would be accepted based on quality and suitability, independent of HCV status. *There would be no intentional utilization of an HCV positive donor into an HCV negative recipient.*

Design & Procedures

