Prospective, open-label study evaluating feasibility, safety and efficacy of Epclusa treatment in lung transplant recipients. Lung transplant recipients who are chronically infected with hepatitis C virus will be treated with Epclusa for 12 weeks and evaluated for evidence of hepatitis C virus in their blood at 12, 24 and 48 weeks after therapy initiation.

Individuals with chronic hepatitis C infection will be enrolled prior to transplant. Participation in this study will allow individuals with active chronic hepatitis C infection to be considered for candidacy for lung transplant, as chronic HCV infection has, until this study, been considered a contraindication for lung transplant at Duke.

Once the subject has undergone lung transplant, been discharged from the hospital and clinically stabilized (a process that can take weeks to months, depending on complications associated with this lung transplant), the subject will be referred for treatment screening. A regaining of functional status, increasing independence in activities of daily living, and a lack of significant or poorly controlled acute infections or need for hospitalization are markers of clinical stability which will be determined by the treating transplant pulmonologist.

If eligible, the subject will then be given study drug which will be taken for 12 weeks. Subject will be monitored throughout treatment course for adverse events. Upon completion of therapy, repeat testing will be performed to assess for clearance of the virus from the blood. Subjects will be followed for 48 weeks after initiation of study drug to monitor for recurrence and to evaluate change in degree of liver stiffness, as assessed by transient elastography.

Regimen (drug/dose/frequency)

Epclusa (sofosbuvir 400mg/velpatasvir 100mg) 1 tablet PO or VT daily x 12 weeks, taken with or without food.

Projected duration of treatment

12 weeks

Projected duration of enrollment

2 years

Study Details

- Treating pulmonologist will refer for treatment screening visit when clinically appropriate. Repeat HCV PCR and genotyping will be done prior to start of Epclusa treatment as part of the treatment screen.

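### SVR12 is worded two ways, and no planned result gives the share of transplanted subjects who end up cured

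*Combined protocol and SAP*

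**What the plan says.** **Meaning of SVR12.** The Primary objectives state: "SVR 12 is the absence of detectable hepatitis C virus in the blood after 12 weeks of antiviral therapy". Background & Significance, describing published response rates, uses a result below the lower limit of quantification (LLOQ) "12 weeks after completion of therapy (SVR12"). The Schedule of Assessments has HCV PCR at Weeks 12, 24 and 48 from the start of treatment, with visits allowed 21 days either side.

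**Who is counted.** The primary endpoint is "Sustained Virologic Response 12 weeks (SVR 12) in those treated with EPCLUSA". The secondary virologic endpoint is "Serum HCV RNA levels at 12-, 24-, and 48-weeks after initiation of EPCLUSA". Two other primary endpoints stand beside SVR12: adverse events that end treatment, and "Eligibility for EPCLUSA treatment within 12 months of lung transplant", which the protocol explains in terms of renal function and drug interactions. Patient survival at 90 days and 1 year is secondary.

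**The goal.** Background & Significance asks whether transplanting candidates with chronic HCV and then "treating them post-transplant with Epclusa is feasible, safe and effective at curing HCV". Deferral is deliberate: "The reason to wait until after lung transplant to treat the hepatitis C virus is two-fold". Design & Procedures enrols subjects before transplant and refers them for treatment screening only once they have "been discharged from the hospital and clinically stabilized (a process that can take weeks to months"). Study Details adds that subjects needing amiodarone must be off it for 60 days before they are eligible.

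Data Analysis & Statistical Considerations promises descriptive and non-parametric methods. It names no analysis set for SVR12 and no rule for missing results, deaths or subjects never treated.

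**The concern.** There are two separate problems.

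First, a primary endpoint can be read off two different samples against two different thresholds. Both samples will be collected, so the choice could be made after the results are known. Under the literal reading of the objectives, a subject who is clear at the end of treatment and relapses afterwards would count as a sustained response.

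Second, the goal is about a strategy, and recipients who never reach treatment are part of that strategy's result. The protocol itself expects obstacles between transplant and treatment. Yet every post-treatment cure measure starts from the treated subjects, so none of them falls when a transplanted subject goes untreated. A treated-only figure of 100% could be quoted as the cure rate of the strategy.

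**Working it through.** The documents give no power, precision or attrition figure, so there is none to reproduce. The check is calendar arithmetic on the schedule, then denominator arithmetic on assumed counts.

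**1. Where each SVR12 reading falls.** Inputs: a 12-week course and visits at ±3 weeks.

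| Reading | Sample | Weeks after end of an uninterrupted course | Range with ±3 weeks | Threshold |
|---|---|---|---|---|
| Primary objectives, literal | Week 12 | 12 − 12 = 0 | −3 to +3 | undetectable |
| Background & Significance | Week 24 | 24 − 12 = 12 | 9 to 15 | below LLOQ |

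The readings are 12 weeks apart. Under the second, a permitted early visit (Week 21) is only 21 − 12 = 9 weeks after treatment.

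**2. Effect of interruptions.** Temporary interruption is a secondary endpoint, so it is expected. If an interruption delays the last dose by *d* weeks, a nominal Week 24 sample falls 12 − *d* weeks after it, which is under 12 for any *d* above zero. The Week 48 sample, even at its earliest (Week 45), is at least 12 weeks after any last dose taken by Week 45 − 12 = 33, a delay of up to 33 − 12 = 21 weeks. It can therefore serve as the fallback.

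**3. Treated-only against all transplanted.** With never treated counted as not cured:

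SVR12 among all transplanted = share treated × SVR12 among treated.

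Assumptions: all 10 enrolled are transplanted, and every treated subject is cured. Intervals are exact (Clopper-Pearson) 95%.

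| Treated | Among treated | Among all transplanted |
|---|---|---|
| 10 | 10/10 = 100% (69.2 to 100) | 10/10 = 100% (69.2 to 100) |
| 9 | 9/9 = 100% (66.4 to 100) | 9/10 = 90% (55.5 to 99.7) |
| 8 | 8/8 = 100% (63.1 to 100) | 8/10 = 80% (44.4 to 97.5) |
| 7 | 7/7 = 100% (59.0 to 100) | 7/10 = 70% (34.8 to 93.3) |
| 5 | 5/5 = 100% (47.8 to 100) | 5/10 = 50% (18.7 to 81.3) |

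Using the 94 to 99% response range in Background & Significance instead, 80% treated gives 0.80 × 0.94 = 75% to 0.80 × 0.99 = 79%.

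**4. Missing results.** If one of 7 treated subjects has no SVR12 result and the rest are cured, the rate is 6/6 = 100% (54.1 to 100) or 6/7 = 85.7% (42.1 to 99.6), depending on a rule the plan does not state.

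**5. Timing from transplant.** A start at month 12 (about week 52) with an uninterrupted course puts the Week 24 sample at 52 + 24 = week 76, or 79 with the visit window. If the Week 48 sample is needed, it falls at 52 + 48 = week 100, or 103 with the window. A fixed cut-off at week 79 would score some interrupted courses as failures through timing alone.

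**The case against.** **The existing endpoints already cover the goal.** Feasible, safe and effective map onto eligibility, discontinuation for adverse events, and SVR12 in the treated. Renal and drug-interaction barriers, including amiodarone, would show in the eligibility result, and deaths would show in survival. Much of this stands, and it limits the concern. What remains is that eligible is not the same as started, and started is not the same as cured. Subjects who are never referred, or who are eligible but never start, have no clear place, and separate eligibility and survival rates do not determine the joint result.

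**The goal sentence is background, and the formal objective is SVR12 in treated recipients.** This is true. A reader might infer that the treated-only primary endpoint is wrong. The documents do not support that: it matches the second primary objective and should stay.

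**Anyone with the counts could work out the rate.** This holds only if the counts are reported, and only with rules for late starters, deaths and missing results, which the plan lacks.

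**Not every virologic measure depends on treatment.** Correct: HCV PCR is also scheduled at transplant evaluation and at treatment screening. The point is confined to measures of cure.

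**The SVR12 conflict may be loose wording.** The objectives call SVR12 the standard outcome, and the Background text describes published results. That may well show what was intended, but the sentence written as the definition does not say it.

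**Conclusion.** Both parts hold, in limited form.

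The SVR12 wording needs correction whatever denominator is used. Read literally, the Primary objectives would report end-of-treatment response as SVR12, 12 weeks earlier than the Background definition and at a different threshold. A reader might infer that the sponsor intends to use the Week 12 sample. The documents do not show this; they show only that the text permits it.

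On the denominator, the plan lacks one descriptive result that its stated goal calls for. The size of the gap is unknown. It is 20 percentage points in the assumed case of 10 transplanted and 8 treated and cured, and zero if everyone transplanted is treated. At these numbers the intervals overlap widely, so the row describes the outcome and supports no formal comparison. Because enrolment precedes transplant and does not guarantee it, the real denominator may also be below 10. A reader might infer that attrition would go unseen. It would not, since eligibility and survival show part of it.

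**What to change.** 1. Correct the Primary objectives to match Background & Significance: SVR12 is HCV RNA below LLOQ at least 12 weeks after the actual last dose. Use the Week 24 sample if it meets this. Otherwise, after an early visit or an interrupted course, use the next scheduled sample (Week 48). Report the Week 12 sample as end-of-treatment response.
2. Keep SVR12 among treated subjects as the primary endpoint, with treated meaning at least one dose and a missing result counted as not cured.
3. Add one descriptive row: SVR12 among all transplanted subjects, with an exact 95% interval. Count as cured those who started within 12 months of transplant and reached SVR12, timed from each subject's own last dose and with no fixed calendar cut-off. The 12-month limit is borrowed from the eligibility endpoint, so state it as a rule of this row. Keep never treated, died, missing and started after 12 months in the denominator as not cured, each on its own line apart from virologic failure. Show the late starters' SVR12 results as well.
4. Record treatment status and the reason for non-treatment at 12 months from the chart review already described under Data collection, storage and confidentiality. The 1-year survival endpoint gives vital status only.

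A subject-flow table and finer eligibility categories would help but are optional.

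**Cost.** Wording, one result row and two chart items; no new visits, tests or subjects. The row could stay open until about week 79 after the last transplant, or week 103 if the Week 48 sample is needed. The figure will be less favourable than treated-only SVR12, and it mixes virologic with non-virologic reasons unless these are itemised.

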- Drug-drug interaction considerations: Many lung transplant recipients develop atrial fibrillation after lung transplant and may require treatment with amiodarone. Due to risk of bradycardia associated with concomitant use of epclusa and amiodarone, subjects must be off amiodarone for at least 60 days in order to be eligible for epclusa treatment.
- After 5 subjects complete 12 weeks of epclusa treatment, a preplanned analysis will be performed to assess safety and efficacy.
- HCV positive donors will have blood collected at time of procurement to be sent for genotyping and quantitative PCR.
- Because Epclusa is FDA-approved for all HCV genotypes, there is no anticipated safety risk associated with the organ donor having a different genotype than recipient.

Early discontinuation

If a subject decides to withdraw from the study prior to completion, the subject will be asked to return for a final visit for data collection.

Selection of Subjects

Inclusion criteria:

1. HCV RNA $\geq 10^3$ IU/ml at screening
2. Chronic HCV infection, defined as positive HCV antibody and/or HCV RNA more than 6 months prior to screening
3. HCV Genotype 1, 2, 3, 4, 5 or 6
4. Otherwise eligible for lung transplant at study site

Exclusion criteria:

1. Age < 18
2. Treatment with any of the following agents:
 - Amiodarone. Subjects previously treated with amiodarone must have stopped the amiodarone at least 60 days prior to day 1 SOF/VEL
 - Carbamazepine, phenytoin, phenobarbital, oxcarbazepine
 - Rifabutin, rifampin or rifapentine
 - HIV regimens containing tenofovir, tipranavir/ritonavir, or efavirenz
 - St John's wort
 - Modafinil

3. Have any serious or active medical or psychiatric illness which, in the opinion of the investigator, would interfere with subject treatment, assessment or compliance
4. Hepatitis B surface antigen positive (This is checked at the time of transplant evaluation.)
. (
5. History of hepatic encephalopathy or variceal hemorrhage
6. Abnormal hematological and biochemical parameters, including:
 - Hemoglobin <8g/dL
 - Platelets <= 50,000/mm³
 - ALT (alanine aminotransferase), AST (aspartate aminotransferase) or alkaline phosphatase >=10 times ULN
 - Total bilirubin >3mg/dL
 - Severe renal impairment, ie creatinine clearance (CrCl) <30mL/min
7. Pregnant women or women planning to become pregnant
8. Women who are breastfeeding
9. Active or recent history (<=1 year) of drug or alcohol abuse

Subject Recruitment and Compensation

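### SVR12, a primary endpoint, is defined at two different times, and neither a labelled sample nor the interim look settles which one applies

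*Combined protocol and SAP*

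**What the plan says.** All references are to the combined protocol and SAP.

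- Purpose of the Study, Primary objectives: "SVR 12 is the absence of detectable hepatitis C virus in the blood after 12 weeks of antiviral therapy". This is the only definition attached to the study's own objectives. The Primary endpoints list names SVR12 without a time origin or an assay threshold.
- Background & Significance, describing published response rates: HCV RNA "less than the lower limit of quantification (<LLOQ) 12 weeks after completion of therapy (SVR12".
- Design & Procedures: subjects are "evaluated for evidence of hepatitis C virus in their blood at 12, 24 and 48 weeks after therapy initiation". The Secondary endpoints list the same three time points again: "Serum HCV RNA levels at 12-, 24-, and 48-weeks after initiation of EPCLUSA". No sample is called the SVR12 sample there, in the visit descriptions or in the Schedule of Assessments.
- Schedule of Assessments: one window of ±21 days covers the study weeks.
- Study Details: "After 5 subjects complete 12 weeks of epclusa treatment, a preplanned analysis will be performed to assess safety and efficacy". The Data Analysis & Statistical Considerations section, which describes a descriptive, unpowered pilot, does not mention this look.

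**The concern.** A sustained response is meant to show that the virus stays away once drug is stopped. An RNA result at the end of a 12-week course cannot show that, because relapse has had no time to appear. Someone who follows the objective literally could take the Week 12 result as the primary outcome. Someone who follows the Background would take Week 24. Both samples exist, so nothing in the data collection would expose the difference.

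The two definitions also differ in threshold, and the visit window allows a Week 24 sample that is too early for the Background definition. The interim look inherits the ambiguity: its efficacy figure could be SVR12, end-of-treatment response or a mixture, and might not be comparable with the final rate.

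**Working it through.** The plan gives no sample-size or precision calculation for SVR12, so there is no figure of its own to reproduce. The check is calendar arithmetic plus one binomial bound.

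**Inputs.** Course of 12 weeks (Regimen). RNA at Weeks 12, 24 and 48 from initiation (Design & Procedures). Window ±21 days = ±3 weeks (Schedule of Assessments). 10 subjects enrolled (Subject Recruitment and Compensation). Look after 5 completers (Study Details). Response of 94–99% in people without decompensated cirrhosis treated for 12 weeks (Background & Significance; not specific to lung recipients).

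**1. Time point.** Objective, read literally: 12 weeks of therapy = Week 12, with 0 weeks off drug. Background: 12 + 12 = Week 24. Both weeks are scheduled for HCV PCR.

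**2. Threshold.** A result that is detected but below the LLOQ is not a response under the objective and is a response under the Background.

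**3. Window.** Earliest Week 24 sample: 24 − 3 = Week 21. Time off drug after a 12-week course: 21 − 12 = 9 weeks, which is 3 weeks short of the Background definition. The upper limit is 24 + 3 = Week 27. The Week 12 sample may fall at 12 − 3 = Week 9, when a subject on schedule is still taking drug.

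**4. The look.** At the moment of the fifth completion, that subject has 0 weeks off drug. The number with SVR12 by the Background definition is therefore at most 4 of 5, and could be 0. The window does not change the maximum: the latest Week 12 visit is Week 15 and the earliest Week 24 visit is Week 21, still 6 weeks apart. Under the literal objective, all 5 could have a result at once.

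Illustration, assuming starts evenly spaced g weeks apart: times off drug are 4g, 3g, 2g, g and 0.
- g = 10.4 (10 starts over 104 weeks): 41.6, 31.2, 20.8, 10.4 and 0 weeks. 3 of 5 have at least 12 weeks, and 4 of 5 have at least 9.
- g of 12 or more: 4 of 5 have at least 12 weeks. This spacing is plausible, because "Individuals with chronic hepatitis C infection will be enrolled prior to transplant" and drug starts only after recovery, so starts can run beyond the two-year enrollment period.

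If the cut-off is the fifth subject's Week 24 sample, 24 − 12 = 12 weeks after the trigger, all 5 can contribute.

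**5. Size.** Let s be the true SVR12 rate and k the number of subjects judged on end-of-treatment RNA alone. Assume that every failure is a relapse after a negative Week 12 sample, so the results are upper bounds. The chance of at least one later failure is 1 − s^k:

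| k | s = 0.99 | s = 0.94 |
|---|---|---|
| 1 | 0.010 | 0.060 |
| 2 | 0.020 | 0.116 |
| 3 | 0.030 | 0.169 |
| 10 | 1 − 0.904 = 0.096 | 1 − 0.539 = 0.461 |

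The k = 10 row is the final analysis if all 10 are treated and Week 12 is reported as SVR12. Each relapse missed moves the rate by 1/10. The rows k = 1 to 3 are a look with that many results pending.

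**The case against.** The strongest reply on the definition is that the objective is only loosely worded. It calls SVR12 the standard outcome in this field, the Background gives the precise meaning, and Week 24 is exactly 12 + 12 weeks. Week 48 follow-up to monitor for recurrence shows that the investigators do not treat Week 12 clearance as final. This makes the Week 24 reading the likelier intention. It does not settle the matter, because the precise wording describes published rates while the objective carries the looser one, and no sample is assigned to the endpoint.

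On the look, the reply largely succeeds. A reader might infer that the interim efficacy analysis must be run with at most 4 of 5 results. The text does not say so: it says after five complete and sets no date, so the sponsor may wait for Week 24. A reader might also infer that subjects who stop early are left out, which would matter because "Adverse events resulting in discontinuation of EPCLUSA" is a primary endpoint. The sentence fixes what prompts the look, not whose data enter it. Nor is a trigger of five completers an error in itself. The study is a descriptive pilot, no decision rule is tied to the look, adverse events are reported separately, and later samples would still catch a relapse for the final result.

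The percentages above are upper bounds. They rest on response rates from other populations and on all failures being relapses.

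**Conclusion.** The inconsistency in the primary endpoint stands and is wrong as written. The objective and the Background can be followed to different samples, 12 weeks apart, with different thresholds, and the window permits a nominal Week 24 sample 3 weeks too early. These findings need no assumption beyond a 12-week course taken on schedule.

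The numerical consequence is modest and uncertain: at most a 10–46% chance that at least one of 10 treated subjects would be classified differently at the two times, under the assumptions stated. The documents do not show that the sponsor intends to report Week 12 as SVR12, only that the wording allows it.

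The interim look is a lesser matter of missing detail: the efficacy measure, data cut-off and analysis set are not stated. The limit of 4 of 5 applies only if data are cut at the fifth completion.

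**What to change.** 1. Correct the sentence in the Primary objectives so that SVR12 is HCV RNA below the LLOQ 12 weeks after completion of therapy, and label the Week 24 sample as the SVR12 sample.
2. Count a sample as SVR12 only if it is taken at least 12 weeks after the last dose actually taken, and change the lower limit of the Week 24 window to match.
3. Report Week 12 RNA as end-of-treatment response, not SVR12, at both the interim and the final analysis, with the actual sampling date relative to the last dose.
4. For the look, the five-completer trigger may stay. Either cut the efficacy data when the fifth subject's SVR12 sample has been taken or was due, or label the efficacy result as end-of-treatment response. Include every subject with at least one dose in the safety summary.
5. State once how subjects who stop, die or have missing samples are classified, and use that rule at both analyses. It must cover early stoppers explicitly, since they can have a sample more than 12 weeks after their last dose.

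The cost is one corrected sentence, a short paragraph in Study Details and one changed window limit. HCV PCR at Weeks 12 and 24 is already scheduled, so usually no sample is added. If the later cut-off is chosen, the interim efficacy summary comes about 12 weeks later. An occasional Week 24 sample must be re-timed. The plan counts "Adverse events requiring temporary interruption in Epclusa therapy" as a secondary endpoint but does not say whether missed doses are made up. If, as an assumed example, 4 weeks were made up, the sample would fall at 12 + 4 + 12 = Week 28, beyond the present limit of Week 27, and might need a separate visit.

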10 subjects will be enrolled. Subjects will be identified during the transplant evaluation phase by the clinical team. The clinical team will assess subject's willingness to participate in the study prior to being approached by the research team. Due to active chronic HCV infection currently being considered a contraindication to transplant at Duke, declining to enroll in the study may impact the subject's candidacy for transplant. The suitability for transplant is ultimately made by the Lung Transplant Team, and dependent on multiple factors. Agreeing to participate in this study is not a guarantee for transplant. Subjects will not be compensated for participating in this study; however, subjects will receive study drug free of charge.

Consent Process – see Section 14 of the e-IRB submission form.

Risk/Benefit Assessment

The most common adverse reactions observed with treatment with EPCLUSa for 12 weeks are headache and fatigue. Bradycardia can occur when taken with amiodarone.

Hepatitis B virus reactivation: There have been case reports of hepatitis B reactivation with Epclusa treatment. All subjects will be screened for hepatitis B prior to enrollment.

Costs to the Subject

There will no additional costs to the subjects as a result of participating in this study. Every attempt will be made to coordinate study visits with routine clinical care.

Data Analysis & Statistical Considerations

This study is a small, pilot feasibility study and therefore not powered for comparative statistics. Descriptive and non-parametric statistics will be performed. A matched, case-control cohort will be based on age and underlying lung disease from same center over same time period will be used to evaluate survival outcomes. An unadjusted Kaplan-Meier survival analysis for cumulative survival will be performed.

Data & Safety Monitoring

In accordance with federal regulations the PI will monitor for, review, and promptly report to the IRB, appropriate institutional officials, sponsor, coordinating center and the appropriate regulatory agency head all unanticipated problems involving risks to subjects or others that occur in the course of a subject's participation in a research, all AE reports will be reported per the DUHS IRB policies.

Data collection, storage and confidentiality

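### The one preplanned aggregate look is counted in subjects who complete 12 weeks of Epclusa, so each discontinuation for an adverse event pushes it later

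*Combined protocol and SAP*

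**What the plan says.** The rule for the look is a single sentence in Study Details: "After 5 subjects complete 12 weeks of epclusa treatment, a preplanned analysis will be performed to assess safety and efficacy". The protocol gives no alternative trigger, such as a number of subjects treated, a calendar date or a number of discontinuations. It does not say whose data enter the analysis, and it attaches no hold or stopping criterion to the result.

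The primary endpoints include "Adverse events resulting in discontinuation of EPCLUSA".

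On numbers, Subject Recruitment and Compensation states "10 subjects will be enrolled", and Design & Procedures states "Individuals with chronic hepatitis C infection will be enrolled prior to transplant". Some of those enrolled may never be treated. The primary endpoints section says: "If subjects do not have adequate renal function or require medications with significant drug interactions with epclusa, they will not be eligible for treatment".

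Outside the look, Design & Procedures says "Subject will be monitored throughout treatment course for adverse events". The visit schedule reviews adverse events at Weeks 4, 8, 12, 24 and 48. Data & Safety Monitoring adds: "In accordance with federal regulations the PI will monitor for, review, and promptly report to the IRB".

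**The concern.** The look is meant to assess safety, but its clock advances only when a subject finishes the course. A subject who permanently stops because of an adverse event has had the primary safety event and, for that very reason, is not counted toward the trigger. The timing of the review is therefore tied to the outcome under review: the more discontinuations there are, the longer the study waits before looking at them together. Early stops for other reasons delay it in the same way.

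At stake is when the pooled assessment of tolerability happens in a population where safety is a stated study question. With at most 10 subjects, and possibly fewer treated, a wait of two or three more subjects is a large part of the study.

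**Working it through.** The protocol derives no power, error rate or sample size, and states the 5 and the 10 without calculation. There is no figure of its own to reproduce.

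**Inputs**
- Completers needed: 5 (Study Details).
- Enrolled: 10 (Subject Recruitment and Compensation). This is the ceiling on the number treated, *n*.
- Early-stop probability per treated subject, *d*: not given. Assumed 10%, 20% and 30%.
- Number treated: not given. *n* = 10 is the best case, and *n* = 6 illustrates loss before treatment.
- Subjects are taken as independent, and as finishing or stopping in the order they start.

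**Step 1: direct counting.** If *k* of the first five treated stop early, the fifth completer can be no earlier than treated subject 5 + *k*. With 2 stops the look waits for at least the 7th treated subject, and with 3 for at least the 8th. With 10 treated, up to 10 − 5 = 5 early stops can accumulate before the look, and 6 or more prevent it.

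**Step 2: are the first five treated enough?** The probability is (1 − *d*)^5:
- *d* = 10%: 0.9^5 = 0.590
- *d* = 20%: 0.8^5 = 0.328
- *d* = 30%: 0.7^5 = 0.168

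If the number treated were not capped, the mean number of subjects completed or stopped by the fifth completer would be 5/(1 − *d*): 5.6, 6.3 and 7.1.

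**Step 3: does the look occur at all?** It does not if there are 4 or fewer completers among *n* treated. The probability is P(X ≤ 4), where X ~ Binomial(*n*, 1 − *d*):

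| *d* | *n* = 10 | *n* = 6 |
|---|---|---|
| 10% | 0.01% | 11.4% |
| 20% | 0.6% | 34.5% |
| 30% | 4.7% | 58.0% |

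With all 10 treated the figure becomes large only at extreme stopping rates (37.7% at *d* = 50%).

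**Step 4: the same quantities under a started-and-resolved trigger.** The look falls when five treated subjects have each completed or stopped, whatever *d* is. It occurs with probability 1 whenever at least five subjects are treated.

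**Step 5: what that trigger cannot repair.** Suppose each of the 10 enrolled is treated with probability 0.6 and, once treated, completes with probability 0.9 (both assumed). Completion per enrolled subject is then 0.6 × 0.9 = 0.54. The chance of no look is P(Binomial(10, 0.54) ≤ 4) = 28% under the present wording and P(Binomial(10, 0.6) ≤ 4) = 17% under the revised trigger. In this example most of the risk of no look comes from loss before treatment, and that part remains.

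**The case against.** The strongest reply is that safety oversight does not depend on this look. A reader might infer that exposure continues unreviewed until five subjects finish. The documents do not support that. Adverse events are followed through treatment and reviewed at every visit from Week 4, and the investigator must review and promptly report unanticipated problems. In an open-label study of 10 subjects, each discontinuation should be visible as it happens. This stands, and it confines the point to the timing of the one pooled assessment.

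A second tempting inference is that poor tolerability would probably cancel the look. With all 10 treated it would not, unless stopping were very common. The chance rises when few enrolled subjects reach treatment, but that loss is not a tolerability effect, and figures that merge the two overstate what the trigger does. This also stands.

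Third, the protocol ties no enrolment hold, dosing pause or stopping rule to the look, so an earlier look has not been shown to interrupt exposure. That is correct. What is gained is an earlier pooled review whose timing does not depend on tolerability.

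Fourth, data from subjects who stopped may be included once the look takes place. The trigger sentence does not exclude them, and subjects who decide to withdraw are asked back for a final data-collection visit (Early discontinuation). Inclusion would improve the content of the look but would not bring it forward.

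Last, the look also serves efficacy, for which counting full courses is a defensible choice. That is a reason to keep a completer summary within the analysis. It does not require completers to set the date of the safety assessment.

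**Conclusion.** The point holds as a fault in the stated rule. That the primary safety event does not advance the count, and so delays the look, follows from the wording and needs no assumed rate.

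The size is mainly delay: at assumed early-stop rates of 10% to 30%, the chance that the look needs more than the first five treated subjects runs from 41% to 83% (1 − 0.590 and 1 − 0.168). Loss of the look is a minor risk with all 10 treated and a material one with only 6. These figures rest on assumed stopping rates, assumed numbers treated, independence, and resolution in order of starting. The documents give no rate for early stopping or for loss before treatment.

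The conclusion does not extend to an absence of safety review, nor to a claim that the present rule leaves subjects exposed who would otherwise have been spared. The change is worth making because the look is already planned and the correction is small.

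**What to change.** Replace the trigger sentence in Study Details with one that performs the preplanned safety and efficacy analysis when five subjects have started Epclusa and each has either reached Week 12 from first dose or permanently stopped, whichever comes first. State that the analysis includes every subject with at least one dose at that date, and that efficacy results are also shown for those who completed 12 weeks. Safety and efficacy then share one trigger, and the protocol settles whose data are used.

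The cost is one or two sentences, with no added visits, tests or subjects. The downside is that the look may contain fewer than five full courses, so its efficacy information may be thinner. The change cannot produce a look if fewer than five subjects ever start Epclusa.
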